#### **10.4.7 Interim Analyses**

No interim analyses are planned.

### **11 COMPLIANCE WITH GOOD CLINICAL PRACTICES, ETHICAL CONSIDERATIONS, AND ADMINISTRATIVE ISSUES**

This study will be conducted in compliance with the protocol, current Good Clinical Practices (GCPs), including the International Conference on Harmonisation (ICH) Guidelines, and in general, consistent with the Declaration of Helsinki. In addition, all applicable local, state, and federal requirements relevant to the use of IP in the countries involved will be adhered to.

#### **11.1 Protection of Human Subjects**

##### **11.1.1 Subject Informed Consent**

Informed consent/assent must take place before any study specific procedures are initiated. Signed and dated written informed consent must be obtained from each subject and/or from the subject's parent or legal guardian prior to enrollment into the study. If the subject is under the legal age of consent, the consent form must be signed by a legal guardian or as required by state and/or local laws and regulations.

All informed consent/assent forms must be approved for use by Ora and receive approval/favorable opinion from an IRB/IEC prior to their use. If the consent form

requires revision (e.g., due to a protocol amendment or significant new safety information), it is the investigator's responsibility to ensure that the amended informed consent is reviewed and approved by Ora prior to submission to the governing IRB/IEC and that it is read, signed and dated by all subjects subsequently enrolled in the study as well as those currently enrolled in the study.

If informed consent is taken under special circumstances (oral informed consent), then the procedures to be followed must be determined by Ora and provided in writing by Ora prior to the consent process.

#### **11.1.2 Institutional Review Board (IRB) Approval**

This study is to be conducted in accordance with IRB regulations (U.S. 21 CFR Part 56.103). The investigator must obtain appropriate IRB approval before initiating the study and re-approval at least annually.

Only an IRB/IEC approved version of the informed consent form will be used.

#### **11.2 Ethical Conduct of the Study**

This study will be conducted in accordance with the ethical principles that originated with the Declaration of Helsinki.

#### **11.3 Subject Confidentiality**

All personal study subject data collected and processed for the purposes of this study should be maintained by the investigator and his/her staff with adequate precautions as to ensure that the confidentiality of the data is in accordance with local, state, and federal laws and regulations.

Monitors, auditors and other authorized representatives of Ora and the IRB/IEC approving this study, the FDA, the DHHS, other domestic government agencies, and other foreign regulatory agencies will be granted direct access to the subject's original medical and study records for verification of the data and/or clinical trial procedures. Access to this information will be permitted to the aforementioned individuals to the extent permitted by law.

A report of the results of this study may be published or sent to the appropriate health authorities in any country in which the IP may ultimately be marketed, but the subject's identity will not be disclosed in these documents.

#### **11.4 Documentation**

Source documents may include a subject's medical records, hospital charts, clinic charts, the investigator's study subject files, as well as the results of diagnostic tests such as X-rays, laboratory tests, and EKGs. The investigator's copy of the CRFs serves as the investigator's record of a subject's study-related data.

#### **11.4.1 Retention of Documentation**

All study related correspondence, subject records, consent forms, record of the distribution and use of all IP, and copies of CRFs should be maintained on file for at least two years after the last approval of a marketing application in an ICH region and until there are no pending or contemplated marketing applications in an ICH region; or until at least two years have elapsed since the formal discontinuation of clinical development of the IP. These documents will be retained for a longer period if required by the applicable regulatory requirements.

If the investigator retires, relocates, or for other reasons withdraws from the responsibility of keeping study records, custody must be transferred to a person who will accept the responsibility.

### **11.5 Labeling, Packaging, Storage, Accountability, and Return or Disposal of Investigational Product**

#### **11.5.1 Labeling/Packaging**

For the run-in period, 1 bottle of will be dispensed for two weeks of BID dosing.

Investigational drug will be packaged and labeled into clinical kits. Study drug will be provided as subjects' kits containing 1 bottle of Naltrexone Ophthalmic Solution or Vehicle Ophthalmic Solution. The required medication until the next visit will be dispensed to the subject (see Section 7.1.2 for details). The kit with remaining medication will be kept at the site.

#### **11.5.2 Storage of Investigational Product**

The IP must be stored in a secure area accessible only to the investigator and his/her designees. The IP will be administered only to subjects entered into the clinical study, in accordance with the conditions specified in this protocol.

Study drug must be refrigerated, protected from light, and secured at the investigational site in a locked container. Subjects should be instructed to store study drug in the same manner, but at room temperature, at home.

#### **11.5.3 Accountability of Investigational Product**

The IP is to only be prescribed by the principal investigator or his/her named sub-investigator(s), and is to only be used in accordance with this protocol. The IP must only be distributed to subjects properly qualified under this protocol to receive IP.

The investigator must keep an accurate accounting of the IP received from the supplier. This includes the amount of IP dispensed to subjects, amount of IP returned to the investigator by the subjects, and the amount returned or disposed upon the completion of the study. A detailed inventory must be completed for the IP.

#### **11.5.4 Return or Disposal of Investigational Product**

All IP will be returned to the sponsor or their designee or destroyed at the study site. The return or disposal of IP will be specified in writing.

#### **11.6 Recording of Data on Source Documents and Case Reports Forms (CRFs)**

The investigator is responsible for ensuring that study data is completely and accurately recorded on each subject's CRF, source document, and all study-related material. All study data should also be attributable, legible, contemporaneous, and original. Recorded datum should only be corrected in a manner that does not obliterate, destroy, or render illegible the previous entry (e.g., by drawing a single line through the incorrect entry and writing the revision next to the corrected data). An individual who has corrected a data entry should make clear who made the correction and when, by adding to the correction his/her initials as well as the date of the correction.

#### **11.7 Handling of Biological Specimens**

Not Applicable.

#### **11.8 Publications**

Authorship and manuscript composition will reflect cooperation among all parties involved in the study.

## 13 APPENDICES

### APPENDIX 1: SCHEDULE OF VISITS AND MEASUREMENTS

Procedure	Visit 1 Day-10 ±1	Visit 2 Day 1	Visit 3 Day 8 ± 1	Visit 4 Day 15 ± 1	Visit 5 Day 29 ±2
Informed Consent	X				
Demographic Data	X				
Medical/Medication History	X				
Medical/Medication History Update		X	X	X	X
Randomization		X			
Urine pregnancy test	X				X
OSDI ® questionnaire	X	X	X	X	X
Ora Calibra ® Ocular Discomfort Scale	X	X	X	X	X
Ora Calibra ® Ocular Discomfort & 4 Symptom Questionnaire	X	X	X	X	X
Visual Acuity Scale (VAS)	X	X	X	X	X
BCVA	X	X	X	X	X
Slit lamp biomicroscopy	X	X	X	X	X
Ora Calibra ® Conjunctival redness	X	X	X	X	X
Corneal Sensitivity (Cochet-Bonnet)	X	X	X	X	X
Tear Osmolarity		X			X
InflammaDry ® (MMP-9) testing		X			X
TFBUT	X	X	X	X	X

Corneal and conjunctival fluorescein staining	X	X	X	X	X
Corneal and conjunctival lissamine green staining	X	X	X	X	X
Schirmer's Test		X	X	X	X
IOP		X			X
Dilated Fundoscopy		X			X
ENK blood draw (optional)					X
Review Eligibility Criteria	X	X	X	X	X
Run-in (vehicle) instillation at study site	X				
Study drug/placebo instillation at study site		X	X	X	X
Run-in (vehicle) Dispensed	X				
Run-in (vehicle) Returned		X			
Adverse Event Query	X	X	X	X	X
Investigational Product Dispensed		X	X	X	
Investigational Product Returned			X	X	X
Dosing Diary Dispensed	X	X	X	X	
Exit from Study					X

## APPENDIX 2: EXAMINATION PROCEDURES, TESTS, EQUIPMENT, AND TECHNIQUES

### *Visual Acuity Procedures (ETDRS Chart)*

LogMAR visual acuity (VA) must be assessed using an Early Treatment Diabetic Retinopathy Study (ETDRS) chart. The procedure used will be consistent with the recommendations provided for using the ETDRS eye chart. VA should be evaluated at the beginning of each visit in the study (i.e., prior to slit-lamp examination). VA testing should be done with most recent correction.

#### Equipment

The VA chart to be used is the ETDRS chart. If smaller reproduction (18" by 18", e.g., from Prevent Blindness) wall charts are used, the subject viewing distance should be exactly 10 feet (or as specified by the manufacturer). In ALL cases, for purposes of standardizing the testing conditions during the study, all sites must use only the 'R' charts, and the right eye should be tested first. For reflectance (wall) charts, the chart should be placed frontally and well-illuminated.

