#### Measurement Technique

The chart should be at a comfortable viewing angle. The right eye should be tested first. The subject should attempt to read each letter, line-by-line, left to right, beginning with line 1 at the top of the chart. The subject should be told that the chart has letters only, no numbers. If the subject reads a number, he or she should be reminded that the chart contains no numbers, and the examiner should then request a letter in lieu of the number. The subject should be asked to read slowly, so as to achieve the best identification of each letter. He/she is not to proceed to the next letter until he/she has given a definite response.

If the subject changes a response (e.g., that was a "C" not an "O") before he has read aloud the next letter, then the change must be accepted. If the subject changes a response having read the next letter, then the change is not to be accepted. The examiner should never point to the chart or to specific letters on the chart during the test.

A maximum effort should be made to identify each letter on the chart. When the subject says he or she cannot read a letter, he or she should be encouraged to guess. If the subject identifies a letter as 1 of 2 letters, he or she should be asked to choose 1 letter and, if necessary, to guess. When it becomes evident that no further meaningful readings can be made, despite encouragement to read or guess, the examiner should stop the test for that eye. However, all letters on the last line should be attempted as letter difficulties vary and the last may be the only one read correctly. The number of letters missed or read incorrectly should be noted.

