### LogMAR Visual Acuity Calculations

The last line in which a letter is read correctly will be taken as the base logMAR reading. To this value will be added the number "N x 0.02" where 'N' represents the total number of letters missed up to and included in the last line read. This total sum represents the logMAR VA for that eye.

For example: Subject correctly reads 4 of 5 letters on the 0.2 line, and 2 of 5 letters on the 0.1 line.

Base logMAR	= 0.1
N (total number of letters incorrect on line 0.2 as well as 0.1)	= 4
N x T (T=0.02)	= 0.08
Base logMAR + (N x T)	= 0.1 + 0.08
logMAR VA	= 0.18

Repeat the procedure for the left eye.

In order to provide standardized and well-controlled assessments of VA during the study, all VA assessments at a single site must be consistently done using the same lighting conditions and same correction if possible during the entire study. If the same correction cannot be used (i.e., a subject forgets his glasses), the reason for the change in correction should be documented.

Note: A clinically significant visual acuity decrease (defined as an increase of 0.22 or greater in logMAR score) from baseline (Visit 1) will be considered an Adverse Event.

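### Both eyes are read on the same 'R' chart, right eye first and with guessing encouraged, so recalled letters can distort left-eye acuity around the 0.22 logMAR adverse-event threshold

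*Combined protocol and SAP*

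**What the plan says.** The visual acuity instructions are in Appendix 2 of the combined protocol and SAP.

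- **Chart and eye order (Equipment).** As a standardisation measure for every case, sites "must use only the 'R' charts, and the right eye should be tested first".
- **Reading (Measurement Technique).** "The subject should attempt to read each letter, line-by-line, left to right, beginning with line 1 at the top of the chart".
- **Unreadable letters (Measurement Technique).** "When the subject says he or she cannot read a letter, he or she should be encouraged to guess".
- **Second eye (LogMAR Visual Acuity Calculations).** After the right-eye score is worked out, the instruction is "Repeat the procedure for the left eye".
- **Scoring and threshold (same subsection).** Each missed letter adds 0.02 logMAR to the value of the last line on which a letter was read. A clinically significant decrease is "defined as an increase of 0.22 or greater in logMAR score) from baseline (Visit 1) will be considered an Adverse Event".

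Appendix 1 schedules best-corrected acuity at all five visits. Section 6.2 lists visual acuity among the safety measures, and Section 10.4.2 has safety endpoints analysed for both eyes. The text gives no second letter set, no change of chart between eyes and no other guard against recall.

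**The concern.** At every visit the subject reads the chart aloud with the right eye. Moments later the subject reads the same letters, in the same order, with the left eye, and is pressed to guess at any that cannot be seen. A letter remembered from the right-eye reading then counts as seen by the left eye.

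This matters most when the two eyes are similar at Visit 1 and the left eye later loses vision while the right does not. At Visit 1 recall has little to add, because the left eye sees nearly everything the right eye read. Later, the letters the left eye has lost are ones the subject has just spoken. The recorded change from Visit 1 then understates the true change, and a loss that meets the protocol's adverse-event definition can go unrecorded under that rule. With about 30 subjects per arm, one subject with a missed event moves an arm's rate by about 1/30 = 3.3 percentage points.

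**Working it through.** **Inputs from Appendix 2.** 0.02 logMAR per letter; threshold 0.22 logMAR above Visit 1; same chart for both eyes; right eye first; guessing encouraged. **Not in the documents:** how many letters a subject recalls. The range of 1 to 4 letters, and the recall fractions in step 4, are assumptions.

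**1. The plan's worked example.** Four of 5 letters are read on the 0.2 line and 2 of 5 on the 0.1 line. Missed letters: 1 + 3 = 4. Score: 0.1 + 4 × 0.02 = 0.18, which reproduces the stated value. One extra correct letter is worth 0.02 even if it opens a new line: the base falls by 0.1 and four misses add 4 × 0.02 = 0.08, a net change of −0.02.

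**2. Threshold in letters.** 0.22 / 0.02 = 11.

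**3. Eyes equal at Visit 1, right eye unchanged, k letters recalled later.** Recorded loss = true loss − 0.02k. The event is missed when the true loss is at least 0.22 and the recorded loss is below 0.22.

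| k (assumed) | Largest true loss missed | Recorded as |
|---|---|---|
| 1 | 0.22 | 0.20 |
| 2 | 0.24 | 0.20 |
| 3 | 0.26 | 0.20 |
| 4 | 0.28 | 0.20 |

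A true loss of 0.30 with k = 4 records as 0.22 and is flagged.

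**4. Recall as a fraction q of the lost letters.** Same setting, each of the L lost letters recalled independently: P(flag) = P(Binomial(L, 1 − q) ≥ 11). Ordinary test-retest error is ignored because the documents give no figure for it.

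| q (assumed) | True 0.22 (L = 11) | True 0.30 (L = 15) | True 0.40 (L = 20) |
|---|---|---|---|
| 5% | 0.57 | 1.00 | 1.00 |
| 10% | 0.31 | 0.99 | 1.00 |
| 20% | 0.09 | 0.84 | 1.00 |
| 30% | 0.02 | 0.52 | 0.95 |
| 50% | 0.00 | 0.06 | 0.41 |

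For example, at q = 10% and L = 11, P(flag) = 0.9^11 = 0.31.

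**5. Right eye already better at Visit 1.** Let g be the right eye's advantage in letters at Visit 1, K the most letters a subject can recall, and d the left eye's true loss in letters, with the right eye unchanged. Recorded loss in letters = d − [min(K, g + d) − min(K, g)]. For d = 12 (true loss 0.24):

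| K | g = 0 | g = 2 | g = 5 |
|---|---|---|---|
| 2 | 0.20, missed | 0.24, flagged | 0.24, flagged |
| 5 | 0.14, missed | 0.18, missed | 0.24, flagged |

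Once g reaches K, recall is the same at both visits and cancels.

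**6. Right eye later falls below the left.** Suppose 3 letters were recalled at Visit 1, so a true left-eye score of 0.20 was recorded as 0.14. Later the right eye is the worse eye and has no extra letters to supply. A true left-eye loss of 0.16 gives 0.20 + 0.16 = 0.36, and the recorded change is 0.36 − 0.14 = 0.22. That is a false adverse event.

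**The case against.** A reader might infer that the error never cancels, always runs towards missing a loss, and lowers sensitivity for every left eye, that is, half of the treated eyes. The documents do not support this. Visit 1 uses the same chart, order and guessing, so recall can already inflate the left-eye starting score when the right eye is better. Unequal eyes can enter: Section 5.4 excludes poor acuity only when both eyes meet the limit. The synopsis excludes it when either eye does, and the two passages need reconciling, but neither requires equal eyes. Steps 5 and 6 show the error cancelling and reversing. Dosing is bilateral, and a loss that affects both eyes alike is not hidden by this route.

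Other objections also have force. The recall rate is unknown and the effect could be negligible. The examiner stops once further attempts are no longer meaningful, which limits the opportunity. The 0.22 rule is not the only way to detect a problem: Section 9.1 treats any clinically relevant deterioration as an adverse event. Adverse-event queries, slit-lamp examination and the OSDI questions on blurred and poor vision occur at every visit, with fundoscopy at Visits 2 and 5. Section 10.4.5 also summarises acuity by visit, although those summaries use the same scores. The procedure is identical in both arms, so a treatment-related bias cannot be inferred.

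Two defences carry less weight. Appendix 2 refers generally to recommendations for the ETDRS chart but does not reproduce them, and the explicit chart rule is the one a site would follow. Standardisation, the stated reason for the rule, is served equally well by a fixed chart for each eye.

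What stands is that the left eye is always tested second on letters just spoken, with no stated guard, and that at the threshold one recalled letter changes the classification.

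**Conclusion.** The concern holds as a small, avoidable weakness in a safety measurement. Left-eye acuity can be contaminated by recall. When the eyes are similar at Visit 1 and only the left worsens, one recalled letter hides a true loss of 0.22, two hide 0.24, and four hide losses up to 0.28. Losses well above the threshold would usually still be flagged; in step 4 a true loss of 0.40 is flagged with probability 0.95 or more unless recall approaches half of the lost letters. With other patterns between the eyes the error can cancel or produce a false event.

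The size rests on an assumed recall of 1 to 4 letters (or 5% to 50% of lost letters), an unchanged right eye and no test-retest error. Neither a between-arm bias nor a general loss of sensitivity in left eyes is shown. The case for acting is that the correction is nearly free.

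**What to change.** Amend the Equipment and Measurement Technique text of Appendix 2 before the first subject's Visit 1, in one of two ways:

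- **Preferred:** each eye has its own fixed letter sequence at every visit, with the 'R' chart kept for the right eye and a second ETDRS letter set used for the left.
- **If only one chart is available:** the left eye reads each line from right to left at every visit, with the reading-direction instruction changed for that eye. This makes recall harder but does not rule it out.

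The documents name only the 'R' charts, so the site should confirm that a second set is available. The cost is one extra chart at a single site, or a small change in technique. Each eye is still compared with itself under constant conditions. Neither option removes learning between visits, because each eye still meets its own letters five times. Any subject already enrolled should stay on the existing procedure so that change from Visit 1 remains comparable.

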#### Measurement Technique

The chart should be at a comfortable viewing angle. The right eye should be tested first. The subject should attempt to read each letter, line-by-line, left to right, beginning with line 1 at the top of the chart. The subject should be told that the chart has letters only, no numbers. If the subject reads a number, he or she should be reminded that the chart contains no numbers, and the examiner should then request a letter in lieu of the number. The subject should be asked to read slowly, so as to achieve the best identification of each letter. He/she is not to proceed to the next letter until he/she has given a definite response.

If the subject changes a response (e.g., that was a "C" not an "O") before he has read aloud the next letter, then the change must be accepted. If the subject changes a response having read the next letter, then the change is not to be accepted. The examiner should never point to the chart or to specific letters on the chart during the test.

A maximum effort should be made to identify each letter on the chart. When the subject says he or she cannot read a letter, he or she should be encouraged to guess. If the subject identifies a letter as 1 of 2 letters, he or she should be asked to choose 1 letter and, if necessary, to guess. When it becomes evident that no further meaningful readings can be made, despite encouragement to read or guess, the examiner should stop the test for that eye. However, all letters on the last line should be attempted as letter difficulties vary and the last may be the only one read correctly. The number of letters missed or read incorrectly should be noted.

### LogMAR Visual Acuity Calculations

The last line in which a letter is read correctly will be taken as the base logMAR reading. To this value will be added the number "N x 0.02" where 'N' represents the total number of letters missed up to and included in the last line read. This total sum represents the logMAR VA for that eye.

For example: Subject correctly reads 4 of 5 letters on the 0.2 line, and 2 of 5 letters on the 0.1 line.

Base logMAR	= 0.1
N (total number of letters incorrect on line 0.2 as well as 0.1)	= 4
N x T (T=0.02)	= 0.08
Base logMAR + (N x T)	= 0.1 + 0.08
logMAR VA	= 0.18

Repeat the procedure for the left eye.

In order to provide standardized and well-controlled assessments of VA during the study, all VA assessments at a single site must be consistently done using the same lighting conditions and same correction if possible during the entire study. If the same correction cannot be used (i.e., a subject forgets his glasses), the reason for the change in correction should be documented.

Note: A clinically significant visual acuity decrease (defined as an increase of 0.22 or greater in logMAR score) from baseline (Visit 1) will be considered an Adverse Event.

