#### **Visit 1 = Day -10 ± 1, Screening**

- Informed consent/Health Information Portability and Accountability Act (HIPAA) consent
- Demographic data, medical/medication, and ocular history
- Urine Pregnancy Test (if applicable)
- Ocular Surface Disease Index (OSDI)
- Ora Calibra® Ocular Discomfort Scale
- Ora Calibra® Ocular Discomfort & 4-Symptom Questionnaire
- Visual Analog Scale (VAS)
- Best Corrected Visual Acuity (BCVA)
- Slit lamp biomicroscopy
- Ora Calibra® Conjunctival redness
- Corneal sensitivity Cochet-Bonnet
- Tear film break-up time (TFBUT)
- Fluorescein staining (Ora Calibra® scale); regions: central, superior, inferior, temporal, nasal, corneal sum, conjunctival sum, and total eye score
- Lissamine green staining (Ora Calibra® scale); regions: inferior, superior, central, temporal, nasal, corneal sum, conjunctival sum, and total eye score)
- Review inclusion and exclusion criteria
- Run-in (vehicle) dose
- Dispense vehicle to all qualifying patients for BID dosing until Visit 2
- Adverse Event Query
- Schedule Visit 2

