#### **Visit 2 = Day 1, Confirmation / Baseline**

- Study Drug Collection
- Medical/medication update
- Adverse event query
- Ocular Surface Disease Index (OSDI)
- Ora Calibra® Ocular Discomfort Scale

- Ora Calibra® Ocular Discomfort & 4-Symptom Questionnaire
- VAS
- BCVA
- Slit lamp biomicroscopy
- Ora Calibra® Conjunctival redness
- Corneal Sensitivity (Cochet-Bonnet)
- Tear Osmolarity
- InflammaDry® (MMP-9) testing
- Tear film break-up time (TFBUT)
- Corneal and conjunctival fluorescein staining
- Corneal and conjunctival lissamine green staining
- Unanesthetized Schirmer's Test
- Intraocular Pressure (IOP)
- Dilated fundoscopy
- Review inclusion and exclusion criteria
- Randomize qualifying subjects
- Study treatment dose
- Dispense study drug/placebo "A" bottle for BID dosing
- Dispense dosing diary
- Adverse Event Query
- Schedule Visit 3

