## 10.4 Statistical Analysis

### 10.4.1 General Considerations

The quantitative variables will be summarized using number of subjects (n), mean, median, standard deviation, minimum and maximum. The qualitative variables will be summarized using counts and percentages.

All summaries will be presented by treatment group.. Summaries will be provided for demographics, baseline medical history, concurrent therapies, and subject disposition.

Baseline measures are defined as the last measure prior to the initiation of study treatment, usually at Visit 2.

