### 10.4.5 Safety Variables

Frequencies and percentages of subjects with treatment-emergent adverse events (TEAEs), serious TEAEs, and TEAEs causing premature discontinuation will be provided by treatment group. An AE is treatment emergent if it occurs or worsens after the first dose of study treatment. Separate summaries will be provided for ocular specific and all AEs (including systemic).

Other safety endpoints including visual acuity, slit-lamp biomicroscopy, corneal sensitivity, dilated fundoscopy, intraocular pressure will be summarized by treatment group and visit using descriptive statistics.

Changes or shifts from baseline will also be summarized where appropriate. For assessments performed by eye, study eye and fellow eye

may be summarized separately. Summaries of the comfort data from the Comfort Assessment of the study will be performed on the safety population from that Assessment. The statistical analysis of safety data will be performed for the safety population, separately for the Comfort Assessment and the Safety and Efficacy Assessment of the study. The analysis of baseline and all efficacy data in the Safety and Efficacy Assessment of the study will be performed for the mITT population. The efficacy analyses may also be performed on the PP population as sensitivity analyses.

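### A visual-acuity adverse event is judged against Visit 1, before the vehicle run-in, while the analysis baseline is Visit 2

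*Combined protocol and SAP*

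**What the plan says.** Appendix 2 (LogMAR Visual Acuity Calculations) gives the site this rule: a "visual acuity decrease (defined as an increase of 0.22 or greater in logMAR score) from baseline (Visit 1) will be considered an Adverse Event". Visit 1 is the screening visit, Day -10 ± 1.

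Section 10.4.1 reads: "Baseline measures are defined as the last measure prior to the initiation of study treatment, usually at Visit 2". The visit list in 8.3.1 carries the title "Visit 2 = Day 1, Confirmation / Baseline". Study treatment also starts there. The Visit 2 list has "Study treatment dose" after randomisation, whereas Visit 1 has only "Run-in (vehicle) dose". The Appendix 1 row "Investigational Product Dispensed" is first marked at Visit 2. Between the two visits every subject uses vehicle in both eyes twice daily for about 10 days.

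Section 10.4.5 counts an AE as treatment-emergent if it begins or worsens after the first dose of study treatment. For the other safety endpoints, VA among them, it says: "Changes or shifts from baseline will also be summarized where appropriate".

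On timing, section 9.3 collects AEs from the first dose of study drug until 30 days after treatment ends. The schedule has "Adverse Event Query" at Visit 1 and again at Visit 2, including once before the randomised dose. The last scheduled contact is the Visit 5 exit, Day 29 ± 2.

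**The concern.** The word baseline points to two visits for one measurement, with the vehicle run-in between them. The hedge in 10.4.1 (usually Visit 2) does not make Visit 1 the baseline. Best-corrected VA is scheduled at every visit, and Appendix 2 has it measured at the start of the visit, so a pre-dose Visit 2 value is planned for every randomised subject.

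The SAP due before unmasking can only partly repair this. It can recompute VA changes, but the site will have applied the Visit 1 rule and recorded AEs visit by visit. A fall that arose mostly on run-in vehicle can enter the treatment-emergent table, and a fall of the full threshold from Visit 2 can miss the numeric rule.

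Safety is part of the study objective, and the only quantitative sample-size statement concerns AE detection. In an arm of 30, one reclassified subject moves an AE proportion by 1/30 = 3.3 percentage points.

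**Working it through.** **The plan's own figures.** The chance of at least one event in an arm of 30 at a true rate of 5% is 1 - 0.95^30 = 78.5%, which reproduces the stated 79%. With 60 it would be 1 - 0.95^60 = 95.4%, so the statement is per arm. Appendix 2 scores 0.02 per letter, so the threshold is 0.22 / 0.02 = 11 letters.

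**Two worked cases (logMAR; higher is worse).**

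| Visits 1, 2, 3 | Visit 3 minus Visit 1 | Visit 3 minus Visit 2 | Appendix 2 rule | Same threshold from Visit 2 |
|---|---|---|---|---|
| 0.10, 0.22, 0.32 | +0.22 | +0.10 | AE | not met |
| 0.22, 0.10, 0.32 | +0.10 | +0.22 | not an AE | met |

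In the first case the rise from Visit 1 to Visit 2 is 0.12, below 0.22. The AE is therefore first met at Visit 3, after study treatment has started, and is treatment-emergent under 10.4.5. In the second case only the general clause in 9.1 on clinically relevant deterioration could make the fall an AE, and that is a matter of judgement.

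**How often this could happen.** The documents give no VA variability, so every input here is an assumption:

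- Normal measurement error with per-visit SD 0.04 to 0.08 logMAR, two eyes with error correlation 0.5, and scores rounded to 0.02; 400,000 simulated subjects.
- Flagged from Visit 1: a rise of at least 0.22 at any of Visits 3 to 5, in an eye not already flagged at Visit 2.
- Flagged from Visit 2: a rise of at least 0.22 at any of Visits 3 to 5.

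With no true change in VA:

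| SD | Subjects of 60 classified differently |
|---|---|
| 0.04 | 0.1 |
| 0.05 | 0.9 |
| 0.06 | 3.3 |
| 0.08 | 10.5 |

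At SD 0.06 the two rules flag similar shares (3.1% from Visit 1, 3.4% from Visit 2), but mostly different subjects.

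If VA worsened by 0.06 (three letters) in the run-in and stayed there, the shares would also differ. From Visit 1 versus Visit 2 they are 6.9% vs 0.8% (SD 0.05), 13.5% vs 3.4% (0.06) and 25.4% vs 13.7% (0.08). For a lasting improvement of 0.06 at SD 0.06 they are 0.4% vs 3.4%.

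**AE window.** Day 1 to Day 29 plus 30 days is 59 days. The last 30 have no scheduled contact: 30/59 = 51% (30/61 = 49% to 30/57 = 53% across the Visit 5 window).

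**The case against.** The strongest reply is that the two passages do different jobs. Appendix 2 tells the site what to record; 10.4.1 defines the baseline for summaries. A pre-vehicle reference captures cumulative loss since study entry, and naming Visit 1 explicitly may be deliberate. In the first worked case VA does worsen after Visit 2, from 0.22 to 0.32, so calling it treatment-emergent is not plainly wrong. The second case would still show in the VA change summary where that is produced.

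Part of this stands. Cumulative loss is worth keeping, and a bare switch to Visit 2 would lose it. The first worked case would then appear neither in the treatment-emergent table nor in a list of falls already met at Visit 2. With SD 0.06 and a lasting worsening of 0.06, roughly 11% to 12% of subjects fall in that gap. But if Visit 1 is deliberate, it should not be called baseline, and nothing in the plan says how such an AE is assigned to run-in or to treatment.

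The magnitude is also fairly criticised: it rests on assumed SDs and shifts, and at SD 0.04 without a shift almost nothing happens. Nor is the 79% figure a measure of precision; it is the chance of seeing at least one event.

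Three stronger readings are tempting, and the documents do not support them:

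- **That run-in AEs are certainly outside the 9.3 window, or that run-in failures enter the safety population.** Both depend on terms. Section 8.5 and the Visit 2 list use study drug for the run-in bottle, and on that reading the early AE queries fit 9.3. Appendix 1 separates run-in vehicle from investigational product, which would keep run-in-only subjects out of the safety population. This is a wording gap.
- **That the 30-day window contradicts the Visit 5 exit.** Spontaneous reports (9.1) and follow-up of open AEs (9.5) can continue after exit. What is missing is a scheduled contact to elicit new events.
- **That the by-arm tables should stop at exit.** That would move later AEs, including serious ones, out of the comparison although they lie inside the 9.3 window.

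**Conclusion.** The conflict is explicit and worth correcting: one measurement has two stated baselines, and the site applies one of them during the trial. The two worked cases need no assumption and show that an AE can be gained or missed because of the choice of visit.

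The size is uncertain. Under the assumed SDs with no true change it runs from about 0.1 to 10.5 of 60 subjects. The larger differences in rates need a lasting VA shift on vehicle, which nothing in the documents suggests.

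A reader might infer that the rule favours one arm. It does not follow: both arms have the same run-in and the same rule. The consequence is misdated or misclassified VA events, not a between-arm bias. The points on run-in terms and on the 30-day window are secondary and call for reconciliation only.

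**What to change.** 1. Reconcile the Appendix 2 note with 10.4.1 so that baseline names one visit. Leave the 0.22 threshold unchanged.
2. In 10.4.5 and the SAP, for the by-arm treatment-emergent tables, judge VA decreases at Visits 3 to 5 against the 10.4.1 pre-dose baseline (Visit 2).
3. List separately every VA decrease of 0.22 or more from Visit 1, at any visit, that does not meet the Visit 2 criterion. This keeps cumulative loss from study entry in view, including the first worked case.
4. Secondary: use one term for the run-in vehicle throughout, so that the start of AE collection in 9.3 agrees with the AE queries at Visits 1 and 2. State in 10.1 and the synopsis that the safety population requires a dose of randomised treatment.
5. Secondary: reconcile the 30-day window in 9.3 with the Visit 5 exit, without removing later AEs from the by-arm tables. Whether to change the window or add a contact is for the sponsor.

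The cost of items 1 to 4 is wording and one extra listing. VA is already measured at all five visits, so no new assessment is needed. Item 5 is also wording only, unless the sponsor chooses to add a contact.
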